## 1. STUDY OBJECTIVES

### Primary outcome

1. Null hypothesis: TAVI/SAVR does not result in a significant change in FFR/RFR 6 months after intervention (Figure 1).
  - a. If the null hypothesis is upheld, this suggests that FFR/RFR measurements in patients with AS is valid even in the presence of severe AS.
  - b. If there is a significant decrease in FFR/RFR 6 months after aortic valve treatment, this suggests that the use of FFR/RFR to evaluate intermediate lesions in patients with severe AS is not valid and requires further investigation.

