### Secondary outcomes

2. Measurement of IMR in patients with AS prior to intervention and 6 months after SAVR/TAVI.
  - a. Description of the range of IMR values in a cohort of patients with severe AS.
    - i. Do all patients with severe AS have high microvascular resistance as assessed by IMR?
    - ii. Does IMR change significantly 6 months after TAVI/SAVR? If there is a significant decrease in IMR then this indicates that microcirculatory function improves 6 months after aortic valve intervention.
3. Null hypothesis: the “corrected” FFR (at baseline; based on baseline IMR) does not correlate with the post-intervention FFR.
  - a. If the null hypothesis is upheld then a correction of FFR using baseline IMR does not improve the validity of FFR in patients with severe AS.
4. Null hypothesis: using IMR at baseline does not improve the ischemia prediction of FFR. Ischemia is measured by SPECT (Figure 2).
  - a. If the null hypothesis is upheld then IMR does not improve stratification of coronary ischemia based on FFR.

- b. If a significant proportion of patients with SPECT ischemia have a raised IMR this would support the hypothesis that IMR can be used to correct falsely high (negative) FFR measurements.
- 5. Comparison of the diagnostic performance of FFR and RFR with SPECT ischemia (and compare with findings of Yamanaka *et al*).
- 6. Reproducibility of the FFR, RFR and IMR

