## Expected outcomes

**Primary outcome:** If the null hypothesis is upheld, this suggests that FFR/RFR measurements are valid even in the presence of severe AS.

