## 9. STATISTICS AND ANALYSIS

### 9.1 Sample Size

The sample size for the ***primary objective*** (change in FFR after aortic valve intervention) is based on previous measurements of FFR in patients with aortic stenosis, where a standard deviation of the data was reported. An expected mean FFR of 0.82 with a standard deviation of 0.08 was used in the calculation. Fifty eight (58) patients with pre- and post-interventions catheterizations will be sufficient to detect a reduction in the FFR from 0.82 to 0.79 with an alpha level of 0.05 and power of 0.80. A total sample of 100 patients with baseline measurements of which 80 patients will undergo (T)AVR without revascularisation (20% will undergo revascularisation) and in this way are eligible for pre-and post-intervention catheterization will allow for a 25 % drop-out during the follow-up phase of the study. Missing values will predominantly be at random. Therefore, the primary endpoint will be assessed using complete case analysis. To account for missing values, the number of patients will be increased from 58 to 80 (since missing data will be excluded from analysis).

For the ***secondary objective*** (comparison of FFR versus RFR): approximately 10-20% will have left main CAD, triple vessel disease, prior myocardial infarction or tandem lesions and will not be eligible for SPECT. One Hundred patients with baseline measurements will allow a 20% drop-out to end up with 80 patients with both baseline SPECT and invasive measurements. Yamanaka *et al.* found that a sample of 80 patients was necessary to determine the optimal cutoff value of iFR for indicating myocardial ischemia. Since RFR and iFR have an extremely high correlation (0.99), the same number of patients (80) is expected to achieve an area under the ROC curve of 0.70 with 0.90% power at a significance level of 0.05 in a 2-sided test.

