### 9.2 Statistical analysis

All quantitative variables will be tested for normal distribution according to the Kolmogorov-Smirnov test. Statistical analyses will be performed via the SPSS statistical software package,

applying a significance level of  $\leq 0.05$ . Continuous variables will be expressed as mean  $\pm$  SD. Comparisons will be done with paired t-, Wilcoxon rank signed, Mann-Whitney U- or Kruskal-Wallis test when appropriate. The chi-square test will be applied for categorical variables and results will be expressed as n (%). Analysis will be performed to compare the intra-coronary measurements (FFR, RFR, IMR) prior to intervention (group 1) versus 6 months after intervention (group 2). Descriptive statistics (mean/median, standard deviation and percentiles for continuous data; percentage for categorical data) and graphical representation (boxplots, histograms and density plots) will be used to compare both groups' characteristics. Intra-coronary measurements in both groups will then be compared and tested using statistical tests (paired t-, Wilcoxon rank signed test). The correlation between FFR and RFR will be analyzed using Pearson correlation coefficient. The diagnostic performance of RFR in indicating SPECT myocardial ischemia will be evaluated using receiver operating characteristic (ROC) curve analysis.

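### The primary test of mean change cannot support the verdicts of valid or not valid that the plan attaches to FFR/RFR in severe AS

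*Combined protocol and SAP*

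**What the plan says.** Section 1 (Study Objectives), Primary outcome, sets a null hypothesis of no significant change in FFR/RFR six months after TAVI or SAVR and fixes two readings in advance.

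- Item 1a, for a non-significant result: "If the null hypothesis is upheld, this suggests that FFR/RFR measurements in patients with AS is valid even in the presence of severe AS".
- Item 1b, for a significant decrease: "this suggests that the use of FFR/RFR to evaluate intermediate lesions in patients with severe AS is not valid and requires further investigation".

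Expected outcomes repeats 1a with no added condition: "If the null hypothesis is upheld, this suggests that FFR/RFR measurements are valid even in the presence of severe AS".

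The pre/post analysis is in section 9.2: "Intra-coronary measurements in both groups will then be compared and tested using statistical tests (paired t-, Wilcoxon rank signed test"). Descriptive statistics and plots accompany it. Section 9.1 sizes the study at 58 pairs to detect a fall from 0.82 to 0.79 with power 0.80: "An expected mean FFR of 0.82 with a standard deviation of 0.08 was used in the calculation".

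Three secondary objectives come near the question of validity:

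- Objective 3 tests the null hypothesis that the corrected "FFR (at baseline; based on baseline IMR) does not correlate with the post-intervention FFR".
- Objective 5 is "Comparison of the diagnostic performance of FFR and RFR with SPECT ischemia".
- Objective 6 is "Reproducibility of the FFR, RFR and IMR".

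None of these is made a condition of 1a or 1b.

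**The concern.** The two readings ask more of the test than it can give.

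1. Failing to reject a null of no change is not evidence of no change. That needs an interval set against a margin, and the plan has neither. The 0.03 in section 9.1 is a difference to detect; nowhere is it called a limit of negligible change.
2. FFR and RFR are used lesion by lesion against cut-offs (0.80 and 0.89 in the Background). A mean change of zero is compatible with many lesions moving up across the cut-off and as many moving down. The same limit applies to 1b: a significant mean fall of any size leads to the not-valid reading, however few lesions change class.

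Whether these indices can be trusted in severe AS is the study's central question. A non-significant primary result would arrive with a favourable answer already written, and a significant fall with an unfavourable one, both on a basis that does not address the question.

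**Working it through.** **Inputs.** From section 9.1: mean FFR 0.82, SD 0.08, change to detect 0.03, alpha 0.05, power 0.80, 58 pairs, 80 eligible patients with 25% drop-out. From the Background: FFR cut-off 0.80. The plan does not say whether 0.08 is the SD at one visit or the SD of the paired change, so a range is shown. If 0.08 is the SD at each visit and rho is the pre/post correlation (an assumption), then

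SD of change = 0.08 × √(2(1 − rho)) = 0.051 (rho 0.8), 0.080 (rho 0.5), 0.095 (rho 0.3).

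**The plan's own figure.** A paired t-test, two-sided 0.05, power 0.80, change 0.03, needs 25 / 58 / 81 pairs at these three SDs. Only 0.08 as the SD of change gives the plan's 58 (power 0.802). The sample size is therefore not in dispute.

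**Point 1: what a non-significant result leaves open (58 pairs).** The 95% half-width is t(57, 0.975) × SD/√58; at SD 0.08 it is 0.021. A fall that just misses significance equals the half-width, so its interval reaches to twice that value. The probability of missing a true fall comes from the noncentral t.

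| SD of change | 0.051 | 0.080 | 0.095 |
|---|---|---|---|
| 95% half-width | 0.0133 | 0.0210 | 0.0249 |
| Largest fall compatible with a just non-significant result | 0.027 | 0.042 | 0.050 |
| P(non-significant), true fall 0.03, 58 pairs | 0.007 | 0.198 | 0.340 |
| Same, 60 pairs (80 × 0.75) | 0.005 | 0.185 | 0.325 |

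At SD 0.08 a true fall of 0.02 is non-significant 54% of the time. Item 1a would read each of these misses as favouring validity.

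**Point 2: what a zero mean change leaves open.** As an illustration, take a bivariate normal with mean 0.82 and SD 0.08 at both visits and one lesion per patient. The cut-off then lies (0.82 − 0.80)/0.08 = 0.25 SD below the mean.

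| SD of change | 0.051 | 0.080 | 0.095 |
|---|---|---|---|
| Patients on opposite sides of 0.80 before and after | 20% | 32% | 39% |
| 95% limits of agreement, ±1.96 × SD of change | ±0.10 | ±0.16 | ±0.19 |

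For comparison, at rho 0.5 a mean fall to 0.79 raises the crossing figure only from 32% to 35%. The mean test barely separates the two situations. Part of the crossing is measurement noise.

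**What an interval rule would deliver.** Take 0.03 as a candidate margin and require the 90% CI to lie within ±0.03. The 90% half-widths are 0.0111 / 0.0176 / 0.0208, so the observed change must be smaller than about 0.0189 / 0.0124 / 0.0092. Results from 1,000,000 simulated trials of 58 pairs:

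| SD of change | 0.051 | 0.080 | 0.095 |
|---|---|---|---|
| CI within margin, true change 0 | >99% | 76% | 54% |
| CI within margin, true change 0.01 | 91% | 58% | 42% |
| Non-significant and CI not within margin, true change 0 | 0% | 19% | 41% |
| Same, true change 0.01 | 0% | 27% | 46% |
| Same, true change 0.02 | 0% | 30% | 46% |

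Item 1b has a counterpart: at SD 0.051, a result is significant with its 90% CI wholly inside ±0.03 in about 22% of trials at a true change of 0.01 and 28% at 0.02. Item 1b would read every such fall as not valid.

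**The case against.** The strongest reply has five parts.

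- **The wording is cautious.** Both items say suggests, and 1b calls for further investigation. True, but the readings are fixed in advance for the primary outcome, and the test does not support even a suggestion about individual lesions.
- **A null result is not expected, and its risk is disclosed.** The Background anticipates a fall in FFR after TAVI, and a 20% miss rate is simply power 0.80. Both stand. Point 1 is ordinary type II error at SD 0.08 and nearly vanishes at 0.051. What remains is the conclusion attached to a miss.
- **Item 1b is the weaker half.** At SD 0.08 the smallest significant fall is 0.021, about 70% of the design effect, and it takes a mean of 0.82 to about 0.80. This stands: a trivially small significant fall is a realistic worry only towards SD 0.051.
- **Other evidence on validity is planned.** The SPECT comparison is the most direct, and section 9.2 adds descriptive summaries. But 1a and 1b do not depend on SPECT, objective 3 is a correlation and not agreement, objective 6 concerns duplicate readings, and separate summaries of each visit do not show paired agreement.
- **Crossing a cut-off does not by itself show invalidity.** Six months of change mixes valve effect, coronary disease and noise, and the Background itself cites different ischaemia thresholds in AS. This stands, and it is why agreement should be descriptive and read with SPECT.

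**Conclusion.** The concern holds and should be fixed. As written, the plan draws a verdict on validity from a test of mean change that cannot deliver one in either direction. The first fault depends on the unknown SD of change: a true fall of 0.03 is missed about 1% / 20% / 34% of the time at SDs of 0.051 / 0.08 / 0.095. The second remains across the whole range, with 20% / 32% / 39% crossing 0.80 at zero mean change. These crossing figures rest on normality, equal SDs at both visits and assumed correlations; they illustrate the size of the problem and do not predict the data. The primary test and the sample size are unaffected.

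**What to change.** Reword 1a, 1b and Expected outcomes together so that neither verdict follows from the mean test alone. Possible text:

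> The mean paired change in FFR is reported with its CI against a margin fixed and justified before analysis. A non-significant change whose 90% CI is not within the margin is called inconclusive. A significant change whose 90% CI is within the margin is reported as detected but smaller than the margin. Any statement on validity is made from the mean change, the pre/post agreement and the SPECT comparison together.

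The design effect of 0.03 is a candidate margin, but the sponsor must justify why smaller changes are negligible. If the signed-rank test is used, the rule should rest on the matching Hodges-Lehmann interval.

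Add to section 9.2, descriptively, the pre/post Bland-Altman limits and the proportion crossing the plan's cut-offs (FFR 0.80, RFR 0.89), with CIs. At 58 pairs the Wilson 95% CI for 19/58 is 22% to 46%. Read these against the same-visit duplicates, single reading against single reading, as a lower bound for noise.

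Keep the FFR and RFR readings separate, with FFR primary as in the Synopsis, the Timeline and section 9.1. RFR would need its own margin. State the power of the interval rule, as tabulated above, rather than enrol more.

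The cost is rewording and a few outputs from data already collected, with no extra patients or procedures. The downside is that some results become inconclusive: with a 0.03 margin and zero true change, about 0% / 19% / 41% at the three SDs.

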### 3. STUDY DESIGN & INTERVENTIONS

#### 3.1 Study Design

A single centre, prospective, cohort study.

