### 3.8 Methodology

Figure 1 summarizes the study flow. Patients admitted electively for a valve work-up and patients admitted through the Emergency department that have to undergo a valve work-up will be approached to take part in the study. All these patients undergo routine cardiac catheterization during preparation for TAVI or SAVR. If they are found to have intermediate coronary artery disease on the angiography, measurements to assess the severity of the lesions and microvascular function (further explained beneath) will be performed during the catheterisation. . Cardiac catheterization is routinely performed in these patients and intra-coronary hemodynamic measurements are routinely used during the assessment of coronary artery disease. SPECT is also used to confirm the presence of ischemia. Baseline intra-coronary measurements of coronary artery disease and coronary microvascular function (IMR) will be carried out in duplicate during the baseline cardiac catheterization if intermediate coronary artery lesions (defined as a coronary artery stenosis in the proximal part of a major coronary artery of 50-90% stenosis by quantitative coronary analysis).

During routine cardiac catheterization, patients with intermediate coronary artery lesions, will undergo hemodynamic assessment of the coronary stenosis according to current ESC guidelines. This entails the use of a pressure wire (Pressure Wire X, Abbott Medical) in the coronary artery distal to the stenosis in order to determine the pressure gradient over the stenosis. Prior to induction of hyperemia, Resting Full cycle Ratio (RFR) is measured before determining fractional flow reserve (FFR). In order to measure a FFR, adenosine at 140 $\mu$ g/kg/min is administered via a peripheral venous infusion catheter. This is routine clinical practice. To address for factors that might cause small changes in these measurements, all measurements will be done twice, without an extra risk to the patient. Two measurements are frequently performed in clinical practice to get a robust measurement. This will also allow us to test the reproducibility of our measurements.

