of risk (the pressure measured by the catheter will simply be recorded for the study data). Immediately following TAVI, intracoronary hemodynamic assessment of the intermediate study lesions will be performed with measurement of FFR, RFR and IMR. For this assessment the same arterial access used during TAVI will be used. Finally, during the six-month cardiac catheterization the coronary artery disease is assessed. During this procedure additional measurements of microvascular function (IMR) will be performed. Again, FFR is routine clinical practice, given the ambiguity of earlier measurements in the presence of aortic valve stenosis, but the additional measurements of IMR will be investigatory. As discussed before the measurements will be performed in duplicate.

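### Rule 1b reads a significant 6-month fall in FFR as evidence against FFR in severe AS, but progression of the untreated lesion would also lower FFR, and section 9.2 makes no use of lesion severity at follow-up

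*Combined protocol and SAP*

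**What the plan says.** Section 3.1 describes the design as "A single centre, prospective, cohort study". There is no concurrent control. The two groups in section 9.2 are the same patients at two times: "prior to intervention (group 1) versus 6 months after intervention (group 2").

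The null hypothesis in Study Objectives, Primary outcome, is that "TAVI/SAVR does not result in a significant change in FFR/RFR 6 months after intervention". Item 1b interprets its rejection: "If there is a significant decrease in FFR/RFR 6 months after aortic valve treatment, this suggests that the use of FFR/RFR" for intermediate lesions in severe AS is not valid and needs further investigation.

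The study lesions are defined in section 3.8 as "50-90% stenosis by quantitative coronary analysis". Section 9.1 limits the paired cohort to patients who have the valve procedure without revascularisation. At follow-up, section 3.8 says that "during the six-month cardiac catheterization the coronary artery disease is assessed", and section 11 defines cardiac catheterisation to include coronary angiography.

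For the before/after analysis, section 9.2 states: "Intra-coronary measurements in both groups will then be compared and tested using statistical tests (paired t-, Wilcoxon rank signed test"). The measurements it names are FFR, RFR and IMR. Change in stenosis appears in no comparison, adjustment or sensitivity analysis.

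One further measurement matters here. The Background, section 3.8 and the section 4 schedule place FFR and IMR immediately after TAVI (section 3.8 adds RFR), and the Background says that this is meant to separate an acute from a chronic effect.

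**The concern.** In a before/after study the patient's own baseline is the only comparator. It isolates the effect of relieving the aortic stenosis only if the coronary lesion itself has not changed. The lesions are 50-90% stenoses left untreated. The interval is longer than 6 months, because baseline is the work-up catheterisation and the 6 months run from the valve procedure. A lesion that tightens in that time lowers FFR whatever happens to the valve or the microcirculation.

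The objectives, expected outcomes and analysis sections do not mention lesion progression. An analyst who followed the plan exactly could therefore report a fall due partly or wholly to progression as evidence against FFR in severe AS. The target change is only 0.03, so a modest drift is not negligible beside it.

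**Working it through.** **Inputs from the documents (section 9.1).** Target fall 0.82 − 0.79 = 0.03; SD 0.08; alpha 0.05; power 0.80; 58 pairs.

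**Step 1: reproduce the plan's figure.** For a two-sided paired t-test with SD of the difference 0.08, the noncentrality at n = 58 is 0.03/0.08 × √58 = 2.86 and the critical value is t(0.975, 57 df) = 2.002. The noncentral t distribution gives power 0.802, and 58 is the smallest n that reaches 0.80. The plan's figure is reproduced when 0.08 is taken as the SD of the paired difference and the test is two-sided. The plan states neither explicitly.

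**Step 2: smallest fall that triggers the rule.** Mean fall = t × SD/√n = 2.002 × 0.08/√58 = 0.021. An observed mean fall of about 0.021 or more counts as a significant decrease.

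**Step 3: progression alone.** The documents give no progression rate, so this step rests on an assumed range: a share p of lesions progresses and each loses d in FFR. The mean shift is p × d, from 0.05 × 0.05 = 0.0025 to 0.20 × 0.15 = 0.03. With zero valve effect, each change is drawn from N(0, 0.08), minus d for the progressing share, in 58 pairs. The table shows the simulated proportion of trials with a significant decrease (t below −2.002). Without progression it is 0.025.

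| Share progressing | Loss 0.05 | Loss 0.10 | Loss 0.15 |
|---|---|---|---|
| 5% (about 3 of 58) | 0.04 | 0.06 | 0.09 |
| 10% (about 6 of 58) | 0.07 | 0.14 | 0.22 |
| 20% (about 12 of 58) | 0.15 | 0.38 | 0.61 |

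**Step 4: a uniform drift, as a cross-check.** With the same n and SD, the noncentral t distribution gives 0.068 for a mean fall of 0.005, 0.153 for 0.01, 0.465 for 0.02 and 0.802 for 0.03. These agree with the table at small shifts. At larger shifts they are somewhat higher, because a mixture of stable and progressing lesions also widens the SD.

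**Step 5: what a formal gate would cost.** If rule 1b also had to hold after excluding changed lesions, power for a true fall of 0.03 would drop from 0.80 at 58 pairs to 0.76 at 52 pairs (about 10% excluded) and 0.70 at 46 pairs (about 20% excluded), before any joint requirement is counted.

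**Step 6: what a concurrent control would cost.** A between-group difference in change of 0.03 with SD 0.08, two-sided 0.05 and power 0.80, needs 112 patients per group. With 58 per group, power is about 0.52.

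**The case against.** Four points can be made for the plan.

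*The rule is hedged.* It needs a significant decrease, says that this suggests a conclusion, and calls for further investigation. A reader might infer that any fall at all would be declared proof that FFR fails in severe AS; the text does not say that. The hedge still does not name progression or plan a check for it.

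*There is a partial safeguard.* A fall already present immediately after TAVI can owe little to progression over the following 6 months. This is a real strength. However, SAVR patients have no such measurement, the Background words it as something that will be tried, and it enters neither rule 1b nor section 9.2. The change from immediately after TAVI to 6 months, which the Background treats as the chronic effect, would still absorb progression.

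*The bias may be small.* This stands. With about three progressing lesions of 58, the chance of a significant decrease is only 0.04 to 0.09. A reader might infer that a few such lesions would be enough to produce the result, but the large figures need about 12 of 58 lesions losing 0.10 to 0.15 each. The documents cannot settle where in the range the truth lies.

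*The absence of a control group is an open design choice.* This also stands. Step 6 shows that a concurrent control would be a different and much larger study, so its absence is not the criticism here.

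A reader might also infer that the corrected FFR would end up correcting for plaque progression. The documents do not support that. The correction is based on baseline IMR, and no formula is given. Progression unrelated to baseline IMR would add noise or shift the intercept, but would not load onto the IMR term.

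**Conclusion.** The concern holds as a gap in interpretation and analysis that is worth closing before the data are analysed. Rule 1b moves from a significant decrease to doubt about FFR/RFR in severe AS without allowing for progression of the lesion, and the plan makes no analytic use of follow-up lesion severity. On the stated assumptions (5-20% of lesions losing 0.05-0.15 FFR, no valve effect, 58 pairs, SD of change 0.08), progression alone would give a significant decrease with probability 0.04 to 0.61 instead of 0.025. The progression figures are assumptions, and the width of that range is part of the finding.

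A reader might go further and infer that the primary conclusion cannot be identified at all. The documents do not support this: the size of the bias is unknown, and the immediate post-TAVI data bear on it. Nor is the sample size in error on this point; 58 is reproduced.

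**What to change.** Keep the paired comparison as the sole primary test.

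- **Section 3.8:** state that percent diameter stenosis of the study lesion is measured on the 6-month angiogram by the same QCA method as at baseline.
- **Section 9.2:** add two pre-specified supporting analyses. (i) The mean FFR change adjusted for change in QCA stenosis, for example by regressing FFR change on stenosis change and reporting the estimate at zero stenosis change. (ii) In TAVI patients, the baseline-to-immediate and immediate-to-6-month FFR changes, reported separately.
- **Rule 1b:** name lesion progression as an alternative explanation for a decrease, to be weighed using (i) and (ii). Do not make them a formal gate, given the power loss in step 5.
- **Any exclusion of changed lesions:** keep it descriptive and symmetric, covering increases and decreases beyond a margin fixed in advance. Removing only lesions that worsened, on a noisy measurement, would tilt the result towards no decrease.

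The cost is QCA reading of angiograms already taken and a little more analysis, with no extra procedure or patients. The limitation is that QCA is imprecise, so the adjustment will be incomplete and should be reported as such.
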